10.2. Screening Failures and Rescreening of Patients

A screen failure is defined as a patient who has given informed consent, and failed to meet the inclusion and/or exclusion criteria. Patients who fail to meet the inclusion/exclusion criteria can be rescreened.

10.3. Induction Period (IP) and Maintenance Period (MP)

Eligible patients will be randomized to treatment group on Day 1. Visits, assessments, and procedures will be performed as per the Schedule of Events in [Table 1](#). Guidelines for dose escalation (Day 1) are provided in [Section 9.6.7](#).

10.4. Open-Label Period (OLP)

Patients who complete the IP and are non-responders at Week 8 and those that complete the MP or experience disease relapse during the MP will have the option to enter the OLP. Patients must

start the OLP within 2 weeks of their Week 8 Induction Visit, Disease Relapse visit in the MP or Week 32 MP visit. Visits, assessments, and procedures will be performed as per the Schedule of Events in [Table 2](#). Guidelines for monitoring patients during dose escalation (Day 1OLP) are provided in Section [9.6.7](#).

The OLP will continue for up to 6 years or until marketing approval of RPC1063 for UC in the country of the clinical site (estimated to be in 2019), or completed transition of patients to Study RPC01-3102, or until the Sponsor discontinues the development program.

10.5. Early Termination

For patients who discontinue the study for any reason, every attempt should be made to complete the assessments detailed in the End of Period/Early Termination (ET) visit and the 30-day and 90-day Safety Follow-up Visits for the collection of safety data and for the assessment of their disease status ([Table 1](#) [IP and MP] and [Table 2](#) [OLP]). With the exception of patients who withdraw consent or are lost to follow-up, central laboratory testing of ALC will continue every 14 days (\pm 3 days) after permanent discontinuation of RPC1063 until it is above the lower limit of normal for patients who discontinue treatment or complete the trial.

10.6. Unscheduled Relapse Assessment Visit

If during the MP or OLP the Investigator becomes aware of a potential relapse outside the normal visit schedule, patients should be evaluated for relapse as outlined in the Schedule of Events ([Table 1](#) [IP and MP] and [Table 2](#) [OLP]).

10.7. Study Stopping Rules

The Sponsor has the right to terminate the study prematurely for safety reasons. In addition, the Sponsor may terminate the study prematurely for administrative reasons. In all cases, all necessary measures have to be taken to guarantee appropriate safety follow-up of all patients already included in the study.

The IEC or IRB and the Regulatory Authorities will be informed in writing about any premature termination of the study.

11. METHODS OF ASSESSMENT

The study design is shown in [Figure 1](#). Assessments and procedures are outlined in [Table 1](#) for the IP and MP and [Table 2](#) for the OLP.

11.1. Efficacy Assessments

11.1.1. Flexible Sigmoidoscopy/Colonoscopy

To ensure quality data and standardization, the same endoscopist should be used throughout the study wherever possible. Colonoscopies will be read blinded to treatment allocation at a centralized reading facility, Robarts Clinical Trials.

11.1.2. Mayo Score

The Mayo score is a standardized, accepted, numerical scale used to evaluate disease severity in people with UC.

The Mayo score consists of four subscores, each ranging from (0-3) for a total score that ranges from 0 to 12:

1. Stool frequency^a
 - 0=Normal number of stools for this patient
 - 1=1 to 2 stools more than normal
 - 2=3 to 4 stools more than normal
 - 3=5 or more stools more than normal
2. Rectal bleeding^b
 - 0=No blood seen
 - 1=Streaks of blood with stool less than half the time
 - 2=Obvious blood with stool most of the time
 - 3=Blood alone passes
3. Findings on endoscopy
 - 0=Normal or inactive disease
 - 1=Mild disease (erythema, decreased vascular pattern, mild friability)
 - 2=Moderate disease (marked erythema, lack of vascular pattern, friability, erosions)
 - 3=Severe disease (spontaneous bleeding, ulceration)
4. Physician's global assessment^c
 - 0=Normal
 - 1=Mild disease
 - 2=Moderate disease

3=Severe disease

- ^a Each patient serves as his or her own control to establish the degree of abnormality of the stool frequency.
- ^b The daily bleeding score represents the most severe bleeding of the day.
- ^c The physician's global assessment acknowledges the three other criteria, the patient's daily recollection of abdominal discomfort and general sense of well-being, and other observations, such as physical findings and the patient's performance status.

Partial Mayo scores are calculated using data from Items 1, 2 and 4 only.

Mayo scores are calculated using:

1. The Stool frequency and rectal bleeding data form the most recent consecutive 3-day period prior to the visit, excluding the following:
 - a. The day medications for constipation, diarrhea, or bowel irregularity are taken
 - b. The day(s) of a procedure or preparation for a procedure (e.g., enemas, other laxative, clear liquid diet) that would affect bowel frequency or blood content of the stool
 - c. The 48 hours following use of anti-motility agents (i.e., loperamide)
 - d. The 48 hours following endoscopy

Disease relapse is defined as when all of the following criteria are met:

- An increase in UC disease activity as defined by an increase in partial Mayo score of ≥ 2 points compared to the Week 8 partial Mayo score with an absolute partial Mayo score ≥ 4 points
- An endoscopic subscore of ≥ 2 points
- Exclusion of other causes of an increase in disease activity unrelated to underlying UC (e.g., infections, change in medication).

11.2. Clinical Safety Assessments

Physical Examination

A complete physical examination will include evaluation of heart, lung, head and neck, abdominal, neurological, full examination of the skin for lesions, and extremities. An interim (or brief) physical examination will include areas with previously noted abnormalities and/or that are associated with any new complaints from the patient. In addition, patients will be questioned on visual symptoms (i.e., blurred vision or decreased visual acuity) during both the complete and interim physical examinations.

All significant findings that are present at screening must be reported on the relevant medical history/current medical conditions eCRF. Significant findings made after randomization that meet the definition of an AE must be recorded on the AEs eCRF.

Height and Weight

Height will be measured at screening. Weight will be monitored throughout the study.

Vital Signs

Heart rate and blood pressure (systolic and diastolic) will be assessed per the Schedule of Events (Table 1 and Table 2).

When obtaining the predose HR and BP during dose escalation (Day 1/IOLP), the patient should rest in the supine position for at least 15 minutes before measurement to establish an accurate baseline measurement. After the patient has been supine for at least 15 minutes, HR and BP will be measured 3 times. An automated validated device can be used, if available. In case the cuff sizes available are not large enough for the patient's arm circumference, a sphygmomanometer with an appropriately sized cuff may be used. The repeat HR and BP measurements will be made at 2-minute intervals. The lowest predose value of supine HR and BP (based on the systolic BP) should be taken as the baseline measure and used for comparison to postdose values. Orthostatic blood pressure will then be measured once with the patient in the standing position (after standing for 2 minutes). A sudden, significant fall in BP (> 20 mmHg) between 2 and 5 minutes after standing from the supine position will be interpreted as orthostatic hypotension and will be documented in the patient chart and eCRF.

Post-baseline HR and BP measurements should be taken after the patient has been supine for at least 5 minutes. HR and BP will be measured once using an automated validated device. Any clinically relevant change from baseline should be confirmed on repeat measures. Orthostatic blood pressure will then be measured in the same manner with the patient in the standing position (after standing for 2 minutes). A sudden, significant fall in BP (> 20 mmHg) between 2 and 5 minutes after standing from the supine position will be interpreted as orthostatic hypotension and will be documented in the patient chart and eCRF.

ECG

12-lead ECG to be performed after the patient has been resting quietly for at least 10-15 minutes. Digital ECG devices will be provided to each clinical site by the central ECG laboratory for the duration of the study. The screening ECG report from the central reader must be available to confirm patient eligibility before randomization. A 12-lead ECG will be performed before and 6 hours after the first dose of investigational drug administration, while the patient is at the clinic.

Detailed instructions describing the process for recording and transmission of the digital ECGs will be outlined in the study-specific manual and provided to the site before the start of the study. Stand-alone ECGs will be obtained, printed, photocopied to preserve the ink if necessary, and kept at the site as source documentation.

ECG & Holter Monitoring

Dual function Digital ECG devices that are capable of capturing both stand-alone ECGs and Holter data will be provided to each clinical site by the central ECG laboratory for the duration of the study. Detailed instructions describing the process for recording and transmission of the digital ECGs and Holter data will be outlined in the study-specific manual and provided to the site before the start of the study.

Stand Alone/Static ECGs

Static ECGs will be captured at intervals as defined in the schedule of assessments (Section 9.1.1). The 12-lead ECG will be performed after the patient has been resting quietly in a supine position for at least 10-15 minutes. The screening 12-lead ECG report from the central reader must be available to confirm patient eligibility before randomization. Six hour post dose ECG will be evaluated by the treating physician or the central reader to confirm if extended monitoring is required. Simultaneously the ECGs will be printed out locally, photocopied to preserve the ink if necessary, and kept at the site as source documentation.

Each ECG tracing should be labeled with the study number, patient initials, patient number, date, and kept in the source documents at the study site. Only clinically significant abnormalities should be reported in the medical history/current medical conditions or AE CRF. Clinically significant findings must be discussed with the Medical Monitor before enrolling the patient in the study.

Continuous 12-lead Holter Monitoring

24 hour continuous cardiac monitoring (12 lead digital Holter monitoring) will be captured at Day 1/IOLP. Holter monitoring will start at least 15 minutes prior to dose and complete at least 24 hours post dose administration. Patients should be in the supine position prior to Holter application through the capture of the static pre-dose 12-lead ECG as well as for the acquisition of the 6 hour post dose 12-lead ECG. Holter analysis parameters will be described in the operations document.

Pulmonary Function Tests

Pulmonary function tests including FEV₁, FVC and DLCO, if applicable, measurements will be performed as scheduled [Table 1](#) and [Table 2](#). These tests will be performed at a qualified pulmonary function laboratory or respiratory department. Please refer to the American Thoracic Society/European Respiratory Society guidelines for standardization of spirometry and single breath determination of carbon monoxide uptake in the lung ([MacIntyre 2005](#); [Miller 2005a](#); [Miller 2005b](#)).

Ophthalmological Examination

OCT will be performed at scheduled times as outlined in [Table 1](#) and [Table 2](#).

Monitoring of AEs and SAEs

Throughout the course of the study, every effort must be made to remain alert to possible AEs or SAEs. Refer to Section 12 for definitions of AEs/SAEs, monitoring, and reporting. Refer to Section 11.5 for monitoring of AEs of special interest.

Monitoring of Concomitant Therapy

The use of concomitant medication and procedures will be monitored throughout the study. Refer to Section 9.8 for prohibited concomitant therapies.

11.3. Laboratory Safety Assessments

Analysis of samples will be conducted centrally by PPD Global Lab. Wherever possible during the Induction and Maintenance Period, Investigators should not send laboratory samples to their local labs as this may lead to unblinding of the treatment assignment given RPC1063's MoA (retention of systemic lymphocytes). Further details of the procedures to be followed for sample collection, storage, and shipment will be documented in a laboratory manual.

Additional and repeat laboratory safety testing may be performed at the discretion of the Investigator.

The following laboratory tests will be performed to assess the safety profile of RPC1063, as outlined in [Table 1](#) and [Table 2](#):

- Routine safety laboratory tests:
 - Hematology – red blood cell (RBC) count, total and differential WBC count (basophils, eosinophils, lymphocytes, monocytes, and neutrophils), platelet count, Hgb, hematocrit, mean corpuscular volume (MCV), mean corpuscular hemoglobin (MCH), and mean corpuscular hemoglobin concentration (MCHC). Total and differential WBC counts will not be provided to the Investigator to maintain the treatment blind during the Induction and Maintenance Period. These parameters and alerts for these parameters will be monitored by the PPD Safety Surveillance team.
 - Blood chemistry - sodium, potassium, chloride, calcium, magnesium, phosphate, blood urea nitrogen, random glucose, albumin, alkaline phosphatase, creatinine, ALT, AST, gamma glutamyltransferase (GGT), amylase, total bilirubin, conjugated bilirubin and CRP. CRP results will not be reported until completion of the study to maintain the treatment blind during the Induction and Maintenance Period. Abnormal laboratory parameters inconsistent with clinical presentation of UC or suspicious of underlying medical condition should be repeated for accuracy. If an increase of amylase above the clinically notable value (≥ 300 U/L) is observed at any post randomization visit, lipase should be tested to determine the origin of elevated amylase (pancreatic versus extra pancreatic).
 - Urinalysis - leukocytes, specific gravity, bilirubin, blood, glucose, ketones, pH, protein, and urobilinogen
- Routine blood samples will be analyzed by the central laboratory. Blood samples taken at the screening visit are to be in the fasting state. Blood samples taken at subsequent visits are recommended to be in the fasting state. Details regarding collection of samples, shipment of samples, reporting of results, laboratory reference ranges, and alerting abnormal values will be supplied to the site before site initiation in a study laboratory manual. The results of the analysis will be made available to

each site by the central laboratory, at the earliest, 48 hours after receipt of the samples by the central laboratory.

- Investigators will be asked to comment on those abnormalities on the respective laboratory result page, including a notation of the clinical significance of each abnormal finding in the patient's source documents. The laboratory sheets will be filed with the patient's source documents. Abnormal laboratory values should not be recorded on the AE eCRF; however, any diagnoses (or signs or symptoms if a diagnosis is not possible) associated with the abnormal findings should be recorded on the AE eCRF.
- Pregnancy test: serum beta-hCG must be performed at screening in women of childbearing potential. Urine beta-hCG will be performed in women of childbearing potential at each scheduled visit. Between scheduled visits up until the 90-day Safety Follow-up Visit, monthly home urine pregnancy tests should be performed by the patient. If a urine pregnancy test result is positive, the Investigator will instruct the patient to suspend further RPC1063 dosing, if applicable, and schedule a follow-up appointment as soon as possible. A serum pregnancy test will be performed for confirmation, including after the 90-day Safety Follow-up Visit, if needed.
- Coagulation panel: prothrombin time (PT) and partial thromboplastin time (PTT). To be performed as scheduled in [Table 1](#) and [Table 2](#).
- Serology testing will be performed at screening to determine the patient's immune status with respect to several viruses; testing will be as follows:
 - anti-VZV IgG
 - HIV antibodies
 - HBsAg and HBcAg IgM
 - anti-HCV IgG or IgM

Patients who are negative for VZV IgG antibodies at screening can undergo vaccination and be randomized 30 days after appropriate VZV vaccination has been completed. Patients testing positive for HIV, or for serological markers of acute or chronic hepatitis B or C, will be excluded from the study unless they are indicative of prior hepatitis B vaccination or cured hepatitis B and accompanied by normal liver transaminase values.

- TB infection: to be assessed using review of the patients' medical history, current physical exam, current screening chest X-ray (if past chest X-rays within 6 months prior to screening is not available) and either a purified protein derivative skin test or a QuantiFERON[®] Gold test for TB. Patients with a positive purified protein derivative may use a QuantiFERON[®] Gold test to confirm the absence of active or latent TB.

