12.1. Adverse Events

The AE definitions and reporting procedures provided in this protocol comply with current CFR 21 Part 312.32. An AE is any untoward medical occurrence that does not necessarily have a causal relationship with the investigational medicinal product. An AE can therefore be any unfavorable or unintended sign, including an abnormal laboratory finding, symptom or disease temporally associated with the use of an investigational medicinal product whether or not considered related to the investigational medicinal product.

UC disease relapse and related symptoms will be monitored as study endpoints, but will not be recorded as AEs.

AEs will be monitored throughout the entire study including the 90-day Safety Follow-up Visit. Investigators will ask the patient at each visit if they have experienced any untoward occurrence since the last study visit. All AEs will be recorded on the eCRFs provided: a description of the event, severity, time of occurrence, duration, any action (e.g., treatment and follow-up tests), and the outcome should be provided along with the Investigator's assessment of the relationship to the investigational drug.

AEs will be recorded from the time written informed consent is signed until 90 days following the last dose of treatment with the investigational drug.

If known, the event diagnosis should be recorded, in preference to the listing of individual signs or symptoms. AEs must be graded as being mild, moderate, or severe and their approximate duration given. Definitions of severity are as follows:

Mild: an AE usually transient in nature and generally not interfering with normal activities;

Moderate: an AE that is sufficiently discomforting to interfere with normal activities;

Severe: an AE that is incapacitating and prevents normal activities.

Even if the Investigator feels there is no relationship to the investigational drug, all AEs MUST be recorded in the eCRF. The Investigator is requested to assess the relationship of any AEs to treatment using the following definitions:

Unrelated: those AEs which are clearly and incontrovertibly due to extraneous causes (concurrent drugs, environment etc.) and do not meet the criteria for drug relationship listed under Unlikely, Possible, Probable or Related.

Unlikely: an AE may be considered unlikely if it includes at least the first two features:

- It does not follow a reasonable temporal sequence from administration of the drug.

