12.6. Clinical Laboratory Parameters and Abnormal Laboratory Test Results

Clinically significant changes, in the judgment of the Investigator, in laboratory parameters (abnormalities) will be recorded as AEs.

During the treatment period, all Total WBC and WBC differential results will be blinded. Reductions in ALC levels is a known pharmacodynamic effect of RPC1063. If any of the following results are observed, the Investigator will be notified and asked to repeat the laboratory tests within approximately 7 days:

- Absolute lymphocyte count [ALC] < 200 cells/ μ L
- Absolute neutrophil count [ANC] < 1000 cells/ μ L
- Total WBC > 20,000 cells/ μ L

If the repeat values also exceed these limits, the Investigator will be informed that the patient's results for the abnormal parameter have fallen below the acceptable threshold.

If ANC or total WBC counts are confirmed below the acceptable limits, the Medical Monitor will contact the treating investigator to request close monitoring for risk of serious infection and appropriate follow-up, at the discretion of the investigator.

If the ALC is confirmed < 200 cells/ μ L, the Investigator will temporarily discontinue investigational drug and then consult with the Medical Monitor. Laboratory testing will be repeated weekly until ALC is > 500 cells/ μ L.

When ALC has returned to > 500 cells/ μ L, the treatment may be reinitiated at the Investigator's discretion (Section 9.6.2 for instructions on resuming treatment after missing doses). For patients whose ALC level is confirmed < 200 cells/ μ L and has not reached the acceptable range (ALC > 500 cells/ μ L) during the study, laboratory testing will be repeated at the 90-day Safety Follow-up Visit.

If patients have elevations in ALT and/or AST \geq 3x the upper limit of normal (ULN), a retest should be performed as soon as possible but not later than 14 days after the original test. If the abnormality is confirmed, weekly testing should continue until ALT and AST are < 3x ULN. If the ALT and/or AST stabilizes at a level > 3x ULN, the Medical Monitor may agree to less

frequent testing. The Investigator should establish causality. In addition, the confirmed elevation $> 3x$ ULN is an adverse event of special interest (see Section 11.5) and should be reported by the Investigator.

At any time, if any of the following occur and there are no apparent alternative causes for the finding, the investigational drug must be permanently discontinued:

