For AE and SAE tables summarizing maximum severity, patients reporting an event more than once with varying severity will be counted only once with the maximum severity within each system organ class/preferred term. For AE and SAE tables summarizing AEs by drug relationship patients will be counted only once, in the category of the strongest relationship to study drug within each system organ class/preferred term.

AEs of special interest will also be summarized by treatment group. The MedDRA SOC and preferred terms that refer to these AEs will be identified by the clinical study team and the project statistician prior to study unblinding and database lock. Treatment-emergent AEs of special interest are defined as AEs related to the following abnormalities:

- Infections
- Bradycardia and heart conduction abnormalities.
- Pulmonary toxicity as measured by the following Pulmonary Function Test (PFT) parameters: FEV₁, FVC, and DLCO.
- Hepatotoxicity which will be assessed by clinical blood chemistry liver function tests.
- Macular edema
- Cutaneous malignancy.

Complete listings of all AEs will be provided. For each AE, the corresponding severity, relationship to study drug, seriousness (yes/no), and available start and stop dates of the event will be specified.

In addition, data listings of all SAEs, AEs leading to discontinuation, and a listings of deaths will also be provided, displaying details of the death captured on the eCRF. Serious adverse event narratives will be provided for the CSR.

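### Protocol 11.3 keeps abnormal laboratory values off the AE form without exception, while 12.6 requires clinically significant changes and confirmed ALT/AST rises above 3 times ULN to be reported, so AE-term counts of such isolated findings depend on which section a site follows

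*Protocol*

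**What the plan says.** Four places in the protocol bear on whether a laboratory abnormality goes on the AE form.

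- Section 11.3, in the bullet on routine blood samples: "Abnormal laboratory values should not be recorded on the AE eCRF". The same sentence then allows that "any diagnoses (or signs or symptoms if a diagnosis is not possible) associated with the abnormal findings should be recorded on the AE eCRF". Investigators note the clinical significance of each abnormal result in the source documents.
- Section 12.6: "Clinically significant changes, in the judgment of the Investigator, in laboratory parameters (abnormalities) will be recorded as AEs". It adds that a confirmed ALT or AST elevation above 3 times ULN "is an adverse event of special interest (see Section 11.5) and should be reported by the Investigator".
- Section 12.1: "An AE can therefore be any unfavorable or unintended sign, including an abnormal laboratory finding". It also makes entry of every AE in the eCRF mandatory.
- Section 9.1.2.1 names liver function test elevation, itself a laboratory result, as the hepatic category of AESI.

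SAP 6.20.1 builds its AE tables from coded terms and selects AESIs by MedDRA system organ class and preferred term. Its hepatic entry reads: "Hepatotoxicity which will be assessed by clinical blood chemistry liver function tests". Separately, SAP 6.20.6 tabulates ALT, AST and GGT by multiples of ULN from the laboratory data.

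**The concern.** A site that follows 11.3 and a site that follows 12.6 will treat the same patient differently. Take a patient with a confirmed ALT rise above 3 times ULN, no symptoms and no diagnosis. Section 11.3 leaves nothing to enter on the AE form; section 12.6 makes the rise a reportable AESI. No passage says which instruction prevails.

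AEs, AEs that lead to stopping drug, and AESIs are named safety endpoints (Protocol 8.2.2), each with its own summary in SAP 6.20.1. An event never entered on the AE form has no coded term and cannot appear in any of them. The discontinuation count is exposed because sections 11.5 and 12.6 tie permanent discontinuation to certain ALT or AST elevations, some of them defined by laboratory values alone. Under 11.3, such a patient could stop drug with no AE on the form.

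**Working it through.** The plan gives no figure to reproduce here, so the check is mainly a comparison of texts.

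**Step 1: where the rules agree.** If a diagnosis, sign or symptom accompanies the abnormal value, 11.3 and 12.6 both put an event on the AE form. If the change is not judged clinically significant and is not a confirmed ALT/AST rise above 3 times ULN, 12.6 does not ask for it to be recorded. Neither case is in conflict.

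**Step 2: where they disagree.** What remains is a value that meets a 12.6 condition but has no accompanying diagnosis, sign or symptom.

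| Isolated finding | Protocol 11.3 | Protocol 12.6 |
|---|---|---|
| Change judged clinically significant | Not on the AE form | Recorded as an AE |
| Confirmed ALT/AST above 3 times ULN | Not on the AE form | Reported as an AESI |

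Section 12.6 does not itself say that the AESI is reported on the AE form, but 12.1 supplies that step by requiring all AEs in the eCRF.

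**Step 3: which SAP outputs depend on the choice.**

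- Dependent: treatment-emergent AE incidence, AESIs, and AEs that led to discontinuation (SAP 6.20.1), since all start from AE-form entries.
- Not dependent: the liver-test table by ULN multiple (SAP 6.20.6). Its category of 3 times ULN or more requires no confirmation and no AE entry, so it would include every patient whose confirmed rise is in the laboratory data.

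**Step 4: illustration of size.**

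Expected recorded hepatic AESIs = n × r × s

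- n = 60, the approximate arm size (Protocol 13.2).
- r = proportion of the arm with a confirmed rise above 3 times ULN, all taken to be asymptomatic and undiagnosed. The plan gives no rate for RPC1063, so 2%, 5% and 12% are assumed. The 12% is the upper figure that Protocol 11.5 gives for liver enzyme elevations above 3 times ULN with fingolimod.
- s = share of patients at sites following 12.6, also assumed.

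| r | s = 0 (all follow 11.3) | s = 0.5 | s = 1 (all follow 12.6) |
|---|---|---|---|
| 2% | 0 | 60 × 0.02 × 0.5 = 0.6 | 60 × 0.02 = 1.2 |
| 5% | 0 | 60 × 0.05 × 0.5 = 1.5 | 60 × 0.05 = 3.0 |
| 12% | 0 | 60 × 0.12 × 0.5 = 3.6 | 60 × 0.12 = 7.2 |

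The laboratory table would be the same in every cell of a given row.

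**The case against.** The best defence is that the sections can be read together. Section 11.3 lets a sign be recorded, and 12.1 describes an AE as "any unfavorable or unintended sign, including an abnormal laboratory finding". In the protocol's own vocabulary, then, a laboratory finding can be a sign: raw values stay on the laboratory page and an event such as raised ALT goes on the AE form when it matters. Other sections lean the same way. Section 12.4 includes laboratory variables in AE monitoring, 12.5 sends AESI-related values to 11.5, and the specific hepatic rule in 12.6 could be taken to override a general sentence about routine samples.

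This shows what the authors probably intended, but it does not remove the conflict. Section 11.3 separates the abnormal findings from the signs or symptoms associated with them. If the finding counts as its own sign, the prohibition in that sentence has no content.

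The second defence is that the SAP already covers the liver. The ULN-multiple table does keep the elevations visible, and that part stands. The table does not replace the AESI count, however: it does not apply the confirmation requirement and carries no investigator assessment of severity or causality. The SAP's hepatic wording could be read as a laboratory-based count, but the same paragraph defines AESIs as AEs selected by coded term. At best the data source is unclear.

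Third, Protocol 9.7.1 requires the reason for stopping drug in the eCRF. That preserves the fact of discontinuation, but does not by itself create a coded AE.

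**Conclusion.** The AE recording rules are wrong as written: they contradict each other for a narrow class of events, and the severity is modest. The affected events are changes judged clinically significant and confirmed ALT/AST rises above 3 times ULN, in each case with no accompanying diagnosis, sign or symptom. For these, the AE-term counts depend on which section a site follows.

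The illustrated difference of 0 against 1.2 to 7.2 hepatic AESIs per 60-patient arm rests on assumed rates and on every such rise being asymptomatic and undiagnosed. It is not an estimate. The documents give no basis for saying how sites would divide.

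A reader might infer more than the documents support:

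- That 12.6 requires every abnormal value to be recorded. It does not; it is limited to the two conditions above.
- That a hepatic signal could disappear from the trial. It could be missing from the AE-term tables, but the laboratory table in SAP 6.20.6 would still show it.
- That the comparison between arms is biased. Sites are blinded, so mixed practice would mainly distort absolute rates and add variation between sites. SAP 6.20 also plans no hypothesis tests on safety results.

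**What to change.** In Protocol 11.3, add an exception to the sentence so that it agrees with 12.1 and 12.6: isolated abnormal values stay off the AE form unless the investigator judges the change clinically significant or the value meets one of the protocol's own AESI criteria.

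In SAP 6.20.1, state that the hepatic AESI count is derived from central laboratory ALT/AST data, using the protocol's criterion of a confirmed elevation above 3 times ULN, as well as from AE terms. The derivation must use retest results, including those from unscheduled visits, because the criterion requires confirmation.

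The cost is one protocol sentence, one SAP derivation from laboratory data already collected, and a few more recorded AEs. Where sites have already recorded events under the present wording, the SAP derivation would still give a uniform hepatic count. It would not recover other clinically significant laboratory changes left off the AE form.
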